6. SPECIFIC AIMS

The purpose of this investigational device study is to collect data to support regulatory submissions, primarily in the United States of America, but it may also be used to support submissions in other regions.

The aim of this study is to better evaluate the efficacy of non-invasive electrical vestibular nerve stimulation (VeNS), together with a lifestyle modification program, as a method of reducing excess body weight, as compared to a sham control and lifestyle modification program.

Primary Objective: Establish the clinical performance of the Vestal device in patients who are overweight.

Secondary Objective: To evaluate the safety of the Vestal device relative to control group, in terms of the occurrence of adverse events, changes from baseline in vital signs (blood pressure and heart rate), and laboratory results in patients who are overweight.

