9. RESEARCH DESIGN AND METHODS

Official Title A randomized, double blind sham controlled clinical trial to evaluate the efficacy of vestibular nerve stimulation (VeNS) (see Appendix 1), combined with a lifestyle modification program (see Appendix 2), compared to a sham control (see Appendix 1) and a lifestyle modification program as a means of reducing excess body weight.

Study Design

- Allocation: Randomized
- Endpoint classification: Efficacy Study
- Intervention Model: Parallel Assignment in 2:1 active to control allocation (Aim to recruit a total of 106 participants overall in the study across two sites, with a dropout allowance of 15% to generate a minimum of 60 active treatment and 30 control subjects). (In order to do this we estimate that we may have to screen up to 150 subjects). The UCSD site will aim to recruit a total of 60 subjects.
- Masking: Double Blind (Subject and all study staff including research dietitian, nursing and Outcomes Assessor)

Pre-screening of Subjects

In order to prevent subjects traveling in needlessly to the study site it is proposed that the study staff allow prospective subjects to pre-screen themselves over the phone. This will involve the study coordinator reading out the inclusion and exclusion criteria to prospective subjects during an initial phone call. The screening questionnaire will not be completed at this stage. Rather the purpose is to make prospective subjects aware as to what the inclusion and exclusion criteria are, since there is no point in them wasting their time and coming in if they are obviously ineligible.

This will also allow study coordinators to provide prospective subjects with a verbal description of the study to the subjects. The text that the coordinator will follow is included for review with this submission.

Overview of Clinical Study

Subject enrollments will be completed during Site Visit 1 (Baseline visit). The ACTRI site can

accommodate up to 3 enrollments per day. All subjects will be part of the study consisting of: Site Visit 1 (~5 hours, 0 months for enrollment); Site Visit 2 (~3.5 hours, 3-month time point); Site Visit 3 (~3.5 hours, 6 months); Site Visit 4 (final visit ~3.5 hours, 12 months); and Home Use Period (12 months).

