Based on the survey of adverse events devised by Utz et al. (2011) occurrence of the following adverse events will be specifically enquired about by the study coordinators during contact with the participants: headache; pain behind the ears; vertigo/ dizziness; blurred vision; nausea; fatigue/ tiredness; seizures; tinnitus; and other symptoms. The coordinators will ask and record whether these symptoms occur: never; almost never; sometimes; almost every time; or every time. And they will ascertain whether they occur while wearing the device, after wearing it, or both. Also, the coordinator will additionally ask whether the participants ever notice skin irritation after wearing the device.

We will monitor each instance of an adverse event causing a dropout from the study. The dropouts, together with causes, will be recorded and reviewed at the end of the study. This guidance from the FDA will be followed: <https://www.fda.gov/downloads/RegulatoryInformation/Guidances/UCM126572.pdf>. If it becomes evident that the proportion of subjects who drop out due to safety concerns/ adverse events convincingly exceeds 30%, the study will be halted.

Hearing Test and Ear Examination

The FDA provided feedback that some study participants should undergo a hearing test and otoscope examination of the ear canal. The FDA were aware that the study had started at this point and as discussed with the FDA there is no suggestion from any of the literature looking at the safety of GVS that hearing or the ear canal are adversely affected (Krystal et al., 2010; Marshall et al., 2010). And that a study specifically looking at the impact of GVS on cochlear function showed no effect (Cevette et al., 2012). Nonetheless, although there is no suggestion that hearing is adversely affected the FDA are requesting that such tests be carried out before agreeing to approve the device.

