Data will be transferred in an encrypted PDF format. Trial staff will be given direction on how to share the trial data and given access to one specific section of a controlled cloud service which is controlled via role based access. Once they have authenticated with the service and the service verifies that they have the correct role to access the system they will be directed to a single webpage within the application where they will be able to upload the encrypted PDF. This PDF is generated on the fly and is therefore not stored in another location that could become compromised. Generating the PDF on the fly means that the source data is extracted from the database, processed and delivered in the context of a single request. This is an important factor as this means that after the request finishes the data in the PDF will not be held in application memory once the request is finished and the data relating to the request is freed. After the PDF is generated it is delivered to the assigned statistician using TLS 1.2 (a strong protocol), ECDHE_ECDSA with X25519 (a strong key exchange), and AES_128_GCM (a strong cipher). These data will be transferred for each subject when they complete participation in the study. If they complete the study protocol this will be at the one-year mark, however, if they drop out early then data accrued up until that point will be sent.

References

STATISTICAL CONSIDERATIONS

These statistical considerations were constructed in conjunction with [name] of the bio-statistics unit at the ACTRI.

Randomization

Treatment assignments will be generated via a randomized block procedure, with block sizes randomly chosen in the set {2, 4, 6, 8, 10, 12}. Subjects will be assigned 2:1 between treatment and control groups. Stratification will be performed by gender and center.

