Methods: Primary Aims

For total body weight loss (TBWL) as a continuous measure, we will use a two-sample t-test to examine the differences between the control and active treatment groups at each time period. We will also build one-sided confidence intervals to test whether the difference between groups exceeds a superiority margin of 5%. As a secondary analysis, we will also use a linear regression with TBWL as the dependent variable and group and other covariates of interest (gender, age, etc.) as independent variables. To assess any longitudinal effects, we will use a linear mixed effects model for weight over time, with fixed covariates for baseline weight, time, group, and a time / group interaction, and a random intercept to account for within-subject correlation. We will use a one-sided exact binomial test to determine if the response rate in the treatment group significantly exceeds 35%, with response defined by a loss of at least 5% of their body weight at the 12-month follow-up. We will also use Fisher's exact test to compare the response rates in each group, and, as a secondary analysis, will consider the use of a logistic regression to control for any other covariates of interest. To investigate possible longitudinal trends, we will fit a logistic mixed effects model, similar to the linear mixed effects model described above.

Methods: Secondary Aims

For each continuous and categorical variable at each time point, we will use a two-sample t-test and Fisher's exact test, respectively. Summary statistics (mean, standard deviation, quantiles, counts, and percentages) and plots will be produced for all demographic and study outcomes. We will investigate the effectiveness of the device by usage by including usage time as a continuous covariate in a linear model for TBWL. CTRI Biostatistics Core personnel will conduct all analyses using the latest version of R (R Foundation for Statistical Computing, Vienna, Austria. <http://www.R-project.org/>). No alpha spending function is applied to adjust for multiple comparisons across the secondary aims, and no claims will be made based on any of the secondary endpoints, which are instead viewed as hypothesis generating endpoints.

Missing Data

The primary hypotheses will be tested on the intent-to-treat population. A sensitivity analysis will be

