performed with the binary weight loss endpoint. This analysis will include a best-case scenario (assuming subjects with missing values have all lost over 5% body weight), a worst-case scenario (assuming no subjects with missing values have lost over 5% body weight), and a tipping point analysis (as described in Yan¹). We will check the assumption that the data is missing completely at random, and use multiple imputation techniques to reduce bias in the estimation of the treatment effect. Missing data will be clearly reported and included in tables.

Power Calculation

The primary outcomes are TBWL from the start of treatment until the 12-month mark and the number of subjects who lose at least 5% of their baseline total body weight. We will power both of these tests at the 0.025 significance level (a Bonferroni correction to maintain a family-wise error rate of 0.05 in our primary analysis). For TBWL, we will test the following null and alternative hypothesis:

$$\begin{aligned} H_0: \mu_t - \mu_c &\leq 5\% \\ H_1: \mu_t - \mu_c &> 5\% \end{aligned}$$

where μ_t and μ_c are the treatment and control mean TBWL in the ITT population. We will use a one-sided two-sample t-test to determine if there is a statistically significant difference in TBWL between our control and treatment arms beyond a superiority margin of 5%. With a total sample size of 90 subjects (30 sham and 60 active treatment), this t-test will have 80% power at the $\alpha = 0.025$ significance level to detect an effect size of $d = 0.63$. Assuming a similar standard deviation of TBWL as the ReShape trial (7.5%), this translates to a detectable difference in TBWL between the treatment and control groups of 4.75%. Assuming this same standard deviation, a two-sample superiority test will have 80% power assuming that the true difference between groups is 6.33%.

For the proportion of treatment subjects who lose at least 5% of their baseline total body weight, we will test the following null and alternative hypothesis:

$$\begin{aligned} H_0: P_t &\leq 35\% \\ H_1: P_t &> 35\% \end{aligned}$$

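### Solicited symptoms are recorded on five ordered levels, but the only test named for categorical secondary variables ignores order if applied to all five, and no per-subject summary is defined

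*Combined protocol and SAP*

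**What the plan says.** Three places in the combined protocol and SAP bear on this.

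- Section 6 states the secondary objective: "To evaluate the safety of the Vestal device relative to control group, in terms of the occurrence of adverse events", together with vital signs and laboratory results.
- Section 9, Safety Endpoints and Adverse Event Monitoring, lists eight named symptoms and a category for others, and sets the response scale: "The coordinators will ask and record whether these symptoms occur: never; almost never; sometimes; almost every time; or every time". Skin irritation is a separate question. The symptom questions are put during contacts with participants. A questionnaire is scheduled at months 3, 6 and 12, with telephone follow-up at week 2 and months 1 and 9.
- Section 9, Methods: Secondary Aims, gives a general rule: "For each continuous and categorical variable at each time point, we will use a two-sample t-test and Fisher's exact test, respectively". It applies no multiplicity adjustment and adds that "no claims will be made based on any of the secondary endpoints, which are instead viewed as hypothesis generating endpoints".

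No ordinal method, cut-point, per-subject summary, significance level or power is given for the symptom data. A chi-square test appears only under Representativeness Analysis, for demographic characteristics.

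**The concern.** Fisher's exact test on a table of two arms by five levels gives the same p-value if the five columns are shuffled. It looks for any difference between the arms. The device effect one would most naturally expect is a move towards more frequent symptoms, and a rank or proportional-odds test aims at that directly. If the general rule is carried over to the symptom scale, the information in the ordering is discarded.

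With about 30 sham subjects there is little power to spare. Section 6 says the data are meant to support regulatory submissions, so a non-significant symptom comparison could be read as reassurance. The silence also leaves the analyst to choose between five levels and yes/no, and to choose any cut-point, after seeing the data.

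**Working it through.** **1. Arm sizes.** The Power Calculation uses 60 active and 30 sham subjects. Its own figure reproduces: for d = 0.63 the noncentrality is 0.63 × √(60 × 30 / 90) = 0.63 × 4.472 = 2.817. At one-sided 0.025 the power is Φ(2.817 − 1.960) = 80.4% by the normal approximation, or 79.6% by the noncentral t, against 80% stated. The recruitment target also reproduces: 90 / 0.85 = 105.9, rounded up to 106.

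**2. What must be assumed.** The documents give no symptom distribution by arm, no safety effect size and no safety significance level. The only symptom rates are 10.2% (itching) and 10.7% (tingling) in Appendix 1. They come from a cited study, are not sham rates and are not on this scale. The sham distributions, the odds ratios (OR) and the two-sided 0.05 level below are therefore assumptions.

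**3. Uniform shift.** At each cut of the scale, odds(active above the cut) = OR × odds(sham above the cut). Example: with 80% of sham answering *never*, the odds of any symptom are 0.20 / 0.80 = 0.25. With OR 3 this becomes 0.75, so 0.75 / 1.75 = 42.9% of active subjects report the symptom and 57.1% answer *never*.

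**4. Simulated power.** There were 1,500 trials per setting, with a Monte Carlo standard error of at most √(0.25 / 1500) = 1.3 points. Each cell gives five-level Fisher / Wilcoxon with tie correction / Fisher on any versus never, in %. Sham percentages run from *never* to *every time*.

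| Sham distribution | OR 2 | OR 3 | OR 4 | OR 6 |
|---|---|---|---|---|
| 90/5/3/1/1 | 3.3 / 15.1 / 11.8 | 12.5 / 38.6 / 33.9 | 25.8 / 61.1 / 57.9 | 61.7 / 89.2 / 86.5 |
| 80/10/6/3/1 | 10.6 / 26.1 / 22.7 | 31.5 / 60.7 / 54.8 | 54.8 / 83.0 / 79.6 | 85.7 / 97.1 / 96.1 |
| 60/20/12/5/3 | 15.9 / 37.7 / 32.1 | 46.3 / 73.5 / 65.4 | 73.7 / 91.1 / 85.0 | 92.9 / 99.1 / 95.6 |
| 40/25/20/10/5 | 22.3 / 40.9 / 27.4 | 53.9 / 77.9 / 54.2 | 76.1 / 93.0 / 73.6 | 94.7 / 99.1 / 87.4 |

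With no effect, the five-level Fisher and Wilcoxon tests reject in 4.5% to 5.5% of trials.

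- *Five-level Fisher against Wilcoxon.* The smallest loss is 99.1 − 94.7 = 4.4 points and the largest is 61.1 − 25.8 = 35.3.
- *Middle of the range.* With sham 70/15/10/3/2, two runs gave 26% vs 51% and 27% vs 52% at OR 2.5, and 40% vs 68% and 39% vs 69% at OR 3. With sham 40/25/20/10/5 they gave 36% vs 61% and 37% vs 62%, then 53% vs 76% and 53% vs 77%. With sham 60/20/12/5/3 at OR 2.5, the result was 30.1% vs 58.1%. The loss is about 23 to 30 points.
- *Any versus never against Wilcoxon.* With at least 60% of sham answering *never*, the loss runs from 97.1 − 96.1 = 1.0 to 73.5 − 65.4 = 8.1 points. With 40% it runs from 99.1 − 87.4 = 11.7 to 77.9 − 54.2 = 23.7.
- *All 106 analysed (71 vs 35), sham 80/10/6/3/1.* Five-level Fisher against Wilcoxon is 12.0% vs 28.9%, 25.3% vs 50.3% and 39.6% vs 67.5% at OR 2, 2.5 and 3, so the picture does not change.

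**5. Effects that are not a uniform shift (60 vs 30).** Here the five-level Fisher test can be the stronger.

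| Pattern | Five-level Fisher | Wilcoxon | Any vs never |
|---|---|---|---|
| Only *almost never* rises | 91.3 | 82.3 | 86.0 |
| Only *sometimes* rises | 93.8 | 89.5 | 85.9 |
| Rise mainly in *every time* | 20.0 | 10.3 | 7.3 |
| Same share with any symptom, frequency moves up | 59.1 | 9.4 | 3.9 |
| Polarised (more *never* and more *every time*) | 92.6 | 8.7 | 14.0 |

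The fourth pattern is still one-directional: sham 60/25/10/4/1 against active 60/10/8/7/15 gives 15% vs 30% at *sometimes* or above and 1% vs 15% at *every time*. Proportional odds fails there because the share with any symptom is equal.

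**The case against.** The strongest reply is that the plan never applies Fisher's test to the five-level data. The general rule does not mention the symptom scale. The symptoms are absent from the secondary outcome list and sit under their own safety heading, and the Belfast data section names safety endpoints as a third class beside primary and secondary. Sections 6 and 9 both speak of occurrence, which a yes/no table fits, and Fisher's test is standard for that. This stands. A reader might infer that the plan commits to a five-level Fisher test; the documents permit that reading but do not establish it. Under the yes/no reading most of the loss disappears when symptoms are uncommon on sham. The 40% *never* setting has 60% of sham users reporting the symptom although the sham delivers no current, so the 12 to 24 point loss may be remote.

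It also stands that no safety hypothesis or power is planned, that secondary endpoints are declared hypothesis generating, and that counts and percentages are promised for all study outcomes. A shift could therefore be seen whatever the p-value. And an ordinal test is not always better, as step 5 shows.

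What the reply does not answer is the gap itself. Neither reading is written down, and answers from several contacts still have no stated route to a single comparison.

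**Conclusion.** The point holds in a conditional form. The scale is ordered, the general rule for categorical secondary variables is order-blind if applied to all five levels, and the plan does not say what will be done. Under a uniform shift, 60 vs 30 subjects and two-sided 0.05, the five-level Fisher test gives up about 4 to 35 points of power, and about 23 to 30 at odds ratios 2.5 to 3 with 40% to 70% of sham answering *never*. Reduction to any versus never gives up about 1 to 8 points, or 12 to 24 if only 40% of sham answer *never*.

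Two stronger conclusions are tempting and not supported. One is that a fixed loss of power is a property of this plan: it depends on sham distributions and odds ratios that the documents do not give. The other is that an ordinal test would make the safety comparison well powered: at odds ratio 2.5, Wilcoxon power of 51% and 61% in the first run of the 70% and 40% *never* settings still means missing a real shift 49% and 39% of the time.

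**What to change.** Add a short paragraph on solicited symptoms to the Statistical Considerations, before unblinding:

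- Define one value per subject and symptom, for example the worst frequency reported over follow-up, and state which contacts count.
- Compare arms with a Wilcoxon rank-sum test or a proportional-odds model, and report the common odds ratio with its 95% confidence interval.
- Show the full five-level counts by arm, and an any-versus-never table with Fisher's exact test.
- State that these comparisons remain hypothesis generating and that a non-significant result is not evidence of no difference.

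The cost is SAP wording; no new data are needed. The price is lower power when the effect is not a uniform shift. The any-versus-never table does not recover a change in frequency among the same share of affected subjects (3.9% power in step 5), which is why the five-level counts should be shown in full.

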- Study participants will be instructed to return home and begin using the device.
- Dietary Counseling from research dietician including review of diet and discussion of Healthwatch 360 app use – 30 minutes.

Summary of the Testing Procedures Visit 1 (0 months)

- Urine pregnancy test (if applicable – i.e. a female of child bearing potential)
- Glucose finger prick (Diabetes screening)
- Check skin behind ears (visual inspection to ensure appears healthy)
- Weight and height to calculate BMI
- Hip and waist measurements
- Fasting Insulin level

- High Sensitivity C-Reactive Protein
- Lipid Panel
- Oral Glucose Tolerance Test (OGTT)
- Pulse rate and blood pressure
- Quality of life survey (Duke University IWQOL – <http://www.qualityoflifeconsulting.com/iwqol-lite.html>)
- DXA Scan (whole body scan)
- Audiogram test including otoscope examination of the ear canals.

Summary of the Testing Procedures Visit 2 (3 months)

- Urine pregnancy test (if applicable – i.e. a female of child bearing potential)
- Weight and BMI calculation
- Check skin behind ears (visual inspection to ensure appears healthy)
- Waist and hip measurements
- Fasting Insulin level
- High Sensitivity C-Reactive Protein
- Lipid Panel
- Oral Glucose Tolerance Test (OGTT)
- Pulse rate and blood pressure
- Quality of life survey (Duke University IWQOL – <http://www.qualityoflifeconsulting.com/iwqol-lite.html>)
- DXA Scan (whole body scan)
- Coordinator asks participant to complete adverse event monitoring questionnaire.
- Audiogram test including otoscope examination of the ear canals.

Other activities at Visit 2 (3 months):

- Dietary Counseling from research dietitian including review of diet reports from Healthwatch 360 app – 15 minutes

Summary of the Testing Procedures Visit 3 (6 months)

- Urine pregnancy test (if applicable – i.e. a female of child bearing potential)
- Weight and BMI calculation
- Check skin behind ears (visual inspection to ensure appears healthy)
- Waist and hip measurements
- Fasting Insulin level
- High Sensitivity C-Reactive Protein
- Lipid Panel
- Oral Glucose Tolerance Test (OGTT)
- Pulse rate and blood pressure
- Quality of life survey (Duke University IWQOL – <http://www.qualityoflifeconsulting.com/iwqol-lite.html>)
- DXA Scan (whole body scan)
- Coordinator asks participant to complete adverse event monitoring questionnaire.
- Audiogram test including otoscope examination of the ear canals.

Other activities at Visit 3 (6 months):

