- Dietary Counseling from research dietitian including review of diet reports from Healthwatch 360 app – 15 minutes

Summary of Final Site Visit 4 (Final Site Visit) (12 months)

- Urine pregnancy test (if applicable – i.e. a female of child bearing potential)
- Weight and BMI calculation
- Check skin behind ears (visual inspection to ensure appears healthy)
- Waist and hip measurements
- Fasting Insulin level
- High Sensitivity C-Reactive Protein
- Lipid Panel
- Oral Glucose Tolerance Test (OGTT)
- Pulse rate and blood pressure
- Quality of life survey (Duke University IWQOL – <http://www.qualityoflifeconsulting.com/iwqol-lite.html>)
- DXA Scan (whole body scan)
- Coordinator asks participant to complete adverse event monitoring questionnaire.
- Audiogram test including otoscope examination of the ear canals.

Other activities at Visit 4 (12 months):

- The study participant will return the investigational device.

Frequency of Follow-Up Appointments

Visits in person at: enrollment (0 months); 3 months; 6 months; and 1 year. Telephone follow up at: weeks 2; months 1 & 9; and as required on an ad hoc basis. There will also be the facility to bring subjects in for review should concerns be raised after the telephone review – e.g. concern re skin irritation behind the ear. Study participants are also free to contact (call or email) study personnel at any time with any issues or inquiries.

Primary Outcome Measures (At 12 months)

- The difference in mean weight loss between the active-product and placebo-treated groups is at least 5% total body weight lost (TBWL), and the difference is statistically significant.
- The proportion of participants who lose 5% or more of baseline body weight in the active-product group is at least 35% and is approximately double the proportion in the placebo-treated group; the difference between groups is statistically significant.

Secondary Outcome Measures (At 12 months)

- The difference in mean percent loss of baseline total body fat in the active versus placebo treated groups. (As measured by means of a whole body DXA scan– see Appendix 4).
- The proportion of subjects who lose at least 5% of baseline total body fat in the active versus placebo treated groups. (As measured by a whole body DXA scan).
- The difference in mean percent loss of baseline truncal body fat in the active versus placebo treated groups. (As measured by a whole body DXA scan).

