Prior to being allowed to start the study proper, potential subjects with type 2 diabetes should be excluded by means of a fasting blood glucose test. This can be via a finger prick sample and glucose meter. Testing should be done in the morning after an overnight fast of at least 8 hours. If the reading is 126 mg/dl or above then the potential subject will be excluded from the study and asked to see their primary care physician in order to be investigated for type 2 diabetes mellitus. The rationale for excluding subjects with type 2 diabetes is explained in Appendix 3. At the same Screen Visit subjects will complete a questionnaire about their medical history and medications to ensure that they fulfil the inclusion and exclusion criteria for the study. The questionnaires will be identified using an alphanumeric code and will not have any identifiable subject data on them. The questionnaires will be securely stored at the ACTRI.

Device Use Procedure

Subjects will be provided with disposable alcohol wipes and asked to clean this area of skin before applying their device. Subjects will also be provided with an adequate supply of disposable 32mm diameter hydrogel electrodes, which are manufactured to go with the device. It is estimated that these electrodes will need to be changed about once a week. The need to change them can be judged by whether they still stick the skin.

The devices come with an instruction sheet indicating that they have buttons on them to increase and decrease the delivered current. Most people can tolerate up to 1.0mA without difficulty and subjects will be encouraged to turn the device up as much as they are comfortable with. Subjects will though be advised that not all users are consciously aware of any stimulation taking place. This is true for some users of the actual device, and also necessary because of the fact that the sham devices will not deliver any electrical current. Subjects can monitor the current being delivered by means of a smart phone app (iOS and Android) that will be installed when they are enrolled in the study. With the sham devices the app will reflect the number of button presses.

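### The device-symptom survey has no Visit 1 baseline, no answer for symptoms unrelated to wearing and no severity grade, so pre-existing symptoms can be reported as device-linked in both arms and can shrink the active-minus-sham difference

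*Combined protocol and SAP*

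**What the plan says.** The secondary objective in Section 6 is a comparison with sham: "To evaluate the safety of the Vestal device relative to control group, in terms of the occurrence of adverse events". For vital signs the same sentence names change from baseline.

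Section 9, Safety Endpoints and Adverse Event Monitoring, lists headache, pain behind the ears, vertigo or dizziness, blurred vision, nausea, fatigue, seizures, tinnitus and other symptoms. The answer format is a frequency: "The coordinators will ask and record whether these symptoms occur: never; almost never; sometimes; almost every time; or every time". The timing follow-up is: "And they will ascertain whether they occur while wearing the device, after wearing it, or both". A question on skin irritation is added. No severity grade, no answer for a symptom unrelated to wearing, and no definition of a new or worsened symptom is given.

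The visit lists in Section 9 carry the line "Coordinator asks participant to complete adverse event monitoring questionnaire" at months 3, 6 and 12. The list headed "Summary of the Testing Procedures Visit 1 (0 months") does not carry it, and the device is handed out at that visit. Between visits the schedule is: "Telephone follow up at: weeks 2; months 1 & 9; and as required on an ad hoc basis". The first scheduled symptom enquiry is thus the week-2 call.

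Two safety domains do have a baseline: the skin behind the ears is inspected and an audiogram is done at Visit 1. Medical history is also taken before the device is used, but for eligibility: "subjects will complete a questionnaire about their medical history and medications to ensure that they fulfil the inclusion and exclusion criteria".

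**The concern.** A subject who had regular headaches, fatigue or tinnitus before enrolment has no record of it on this scale. Use is asked for on at least five days a week, so much of ordinary life falls after a session. When asked at month 3, such a subject may well report the symptom as occurring after wearing. That can happen in both arms.

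Two things are at stake. First, the rate of device-linked symptoms reported in each arm can include symptoms that the device did not cause. Second, a common background leaves fewer subjects in whom the device can show an effect, so a real excess over sham is harder to see with only 30 sham subjects. Section 6 says the data are meant to support regulatory submissions, and a diluted comparison leans towards a finding of no difference in safety.

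Severity is a separate gap. One severe episode of vertigo in a year would be scored near the bottom of the scale, and faint tingling at each session at the top. The order of the scale is an order of frequency, not of harm.

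**Working it through.** **Plan's own figure.** There is none. The documents give no expected rate, power or alpha for the symptom comparison.

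**Inputs from the documents.** 60 active and 30 sham subjects (Power Calculation); planned enrolment 106 (same section); 24 enrolled at the time of writing (Section 8); Fisher's exact test for categorical variables at each time point (Methods: Secondary Aims). If the change were made at once, 106 − 24 = 82 subjects could have a baseline.

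**Assumptions, not in the documents.** Background prevalence b of 20% or 30%; device-caused symptom rate e of 20% or 30%; unrelated new onset of 5% in both arms; two-sided alpha of 0.05; outcome reduced to ever or never reported. A share p of background symptoms persists. A share a of background and unrelated symptoms is reported as device-linked.

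**Step 1: the contrast.** Without a baseline, the sham rate is 1 − (1 − bpa)(1 − 0.05a). The active rate is 1 − (1 − bpa)(1 − 0.05a)(1 − e). The difference is

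(1 − bpa) × e × (1 − 0.05a).

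The factor (1 − bpa) is the dilution. It equals 1 when no background symptom is attributed to the device. It never reverses the sign, and with e = 0 the difference is zero.

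With b = 20%, e = 20%, p = a = 1:
- sham: 1 − 0.80 × 0.95 = 24%
- active: 1 − 0.80 × 0.95 × 0.80 = 39%
- difference: 0.80 × 0.20 × 0.95 = 15 points
- among those symptom-free at baseline: 24% against 5%, a difference of 19 points

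With p = 60% and a = 50%, bpa = 0.20 × 0.6 × 0.5 = 0.06, so the dilution is only 6%.

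**Step 2: power.** Simulation, 6,000 trials per setting. *As listed* compares all subjects on ever reporting the symptom. *Drop* uses only subjects with a known negative baseline. *Keep* removes only subjects known to have had the symptom at Visit 1 and retains those whose baseline is unknown. Exact enumeration of the as-listed test in the first block gives 25%, 20%, 52% and 41%, which agrees.

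| Case | b, e | As listed | Drop | Keep |
|---|---|---|---|---|
| p = 1, a = 1, all have a baseline | 20%, 20% | 25% | 48% | 48% |
| | 30%, 20% | 20% | 44% | 44% |
| | 20%, 30% | 51% | 80% | 80% |
| | 30%, 30% | 41% | 74% | 74% |
| p = 60%, a = 1, 24/106 lack a baseline | 20%, 20% | 36% | 36% | 43% |
| | 30%, 20% | 27% | 28% | 35% |
| | 20%, 30% | 65% | 68% | 74% |
| | 30%, 30% | 55% | 59% | 64% |
| p = 1, a = 50%, 24/106 lack a baseline | 20%, 20% | 43% | 40% | 51% |
| | 30%, 20% | 34% | 30% | 42% |
| | 20%, 30% | 75% | 77% | 83% |
| | 30%, 30% | 64% | 67% | 74% |
| p = 60%, a = 50%, 24/106 lack a baseline | 20%, 20% | 52% | 41% | 55% |
| | 30%, 20% | 45% | 31% | 47% |
| | 20%, 30% | 84% | 77% | 87% |
| | 30%, 30% | 78% | 67% | 80% |

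**Reading.** In the first block the gain is 23 to 33 points; allowing for simulation error, about 22 to 34. In the other blocks *keep* gains 2 to 10 points here and reached about 12 in repeat runs, so about 2 to 12. *Drop* is not safe: in the last block it loses 7 to 14 points, up to 16 in repeat runs.

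**Limit of the model.** Worsening of a baseline symptom is not modelled. Subjects known to have had the symptom leave that symptom's comparison. If they stay in as non-events with no chance of worsening, the gain falls to about 18 to 27 points in the first block and to between −4 and +10 in the others.

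**The case against.** The strongest objection is that the scale is worded per use and the follow-up asks about wearing. A subject whose headaches have nothing to do with the sessions can answer *never*. A reader might infer that every pre-existing symptom must be counted as a device effect; the documents do not support that. This stands. It is why the size depends on a, and why the upper range is a corner case.

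A reader might also infer that the missing baseline could produce a false signal against the device. It does not: randomisation puts the same background in both arms in expectation, and Step 1 gives a zero difference when the device has no effect.

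The background is limited for some items. Vestibular dysfunction, epilepsy, stroke and severe head injury are exclusions in Section 10, and skin and hearing have baselines. The concern is therefore mainly about headache, fatigue and tinnitus. Those are not excluded, and the audiogram as described contains no tinnitus question.

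Severity and relatedness rules may sit in the separate Good Clinical Practice appendix (Appendix 6) or in the FDA guidance cited by link. Neither was available. Either could grade adverse events, but neither is described as adding a symptom survey at Visit 1.

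Finally, one might read the risk/benefit section's description of discomfort as mild as a claim the trial should verify. It is a statement in a risk assessment, not a hypothesis under test, and the point does not rest on it.

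**Conclusion.** The point holds as a gap in the survey with a modest and uncertain effect. The absence of the symptom list at Visit 1, of a *neither* answer and of a severity item is plain in the text supplied. The direction of the dilution is arithmetic once any background symptom persists and is reported as device-linked. Its size cannot be taken from the documents. The range runs from about 2 to 12 points of power under partial persistence or attribution, with 24 of 106 lacking a baseline, to about 22 to 34 points when everything persists, all is attributed and all have a baseline. These figures assume 20% or 30% background and removal from a symptom's comparison of those known to have it at Visit 1. The change is worth making because it is cheap and the plan already takes baselines for skin, hearing and vital signs.

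**What to change.** 1. Give the same symptom list, without the device-timing item, at Visit 1 before the device is handed out. Compare arms on symptoms that are new or worse than at Visit 1. State in advance how a symptom that is present at Visit 1 and unchanged is handled; the gains quoted are for leaving that subject out of that symptom's comparison. Keep subjects enrolled before the change in the comparison with baseline coded as unknown, rather than dropping them, and also report the all-subjects table.
2. Add an answer for *neither, or present before the device* to the timing item.
3. Add a mild, moderate or severe item for each reported symptom, and tabulate the worst severity by arm.

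The cost is a few minutes per visit and a short amendment. The 24 or more subjects already enrolled can have no true baseline. The protocol has made a comparable change before: audiograms were added after enrolment had begun, with earlier enrollees tested at later visits. If the Good Clinical Practice appendix already grades severity, item 3 should use the same grades.
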